Church-based Health Advisors and our Health Practitioner to Deliver Seminar and Workshop (Phase 2): The bi-weekly seminars will be peer-led and conducted by each church-based health educator within their church. In each seminar, one of our specialists will participates in delivering the main component of intervention. For example, the infectious disease expert will help individuals reduce the risk of acquiring COVID-19; the pharmacist will work with participants to enhance their medication adherence and remove barriers related to their refills; and the lifestyle coach will help improve participants' lifestyles; etc.

Hypotheses: As a result of this intervention, it is expected that: 1) A 30% improvement of chronic physical and mental disease management among AA older adults; 2) A 80% increase in knowledge, attitude, and behaviors of COVID risk among AA older adults; and 3) a 40% increase in COVID-19 testing and 4) a 70% increase in uptake of influenza and pneumococcal vaccinations among participants.

Survey Instruments: Per the instruction of this NOSI, we will adopt survey instruments recommended by the **phenX Toolkit and Public Health Emergency and Disaster Research Response**.¹¹⁴ The survey (developed by the Aging and Geriatric Research Institute on UF) includes Covid-19 related measures and Health status and health care utilization, quality of life, and other related variables. In addition, we will include several validated survey instruments that our research team has recently used among AA older adults to investigate health status, health care utilization, and adherence to drug regimes in South Los Angeles.

Sample Size and Data Analysis (Phase 2): We will use a pretest–posttest design, comparing our outcomes before and after the intervention, with a three-month interval. Since our outcomes are binary (COVID infection

status, use of services, medication non-adherence, etc.), we will use the McNemar test, the test of choice for analyzing binary matched-pairs data.¹¹⁵ For our power calculation, we assume that our primary outcome (poor adherence) will show a 36% relative change (considering a 22% baseline

TIMELINE: Activities & Timeline (Months)	1-3	4-6	7-9	10-12
Church leaders recruited	X			
CDC/States Guideline Implementation	X	X	X	X
Health Advisors recruited & trained	X	X		
AA older adults recruited		X	X	X
Baseline data collection (older AA)		X	X	X
IRBNet # 1663247-2 Approved by: CDU IRB				
Older AA Intervention implemented		X	X	
Post intervention data collected & analyzed			X	X
Final reports & RO1 preparation				X

Approval Period: April 23, 2021 to

status). Assuming an alpha of 0.05, we calculate that a total sample of 240 study participants will be necessary to achieve 80% power.¹¹⁶ With 10% drop-out,^{117,118} we will need to enroll 265 individuals. We will conduct longitudinal follow-up assessments to document changes to compare with baseline measures. At the descriptive level, the distribution and frequency of all items will be examined. The main hypothesis of this study is significant improvement of binary and continuous outcomes from pre- to post- tests. In bivariate analysis, we will apply McNemar's test as well as paired t-test to examine improvement of the outcome over the course of the study. Conducting multivariate analysis, when outcome variables are dichotomous/binary, to explore the role of potential confounders and baseline health status, as determinants of response (change), we will apply logistic regression. However, for corresponding dependent variables that appear to be ordinal a logit link will be used in polytomous or ordinal logistic models. Additionally, for continuous outcomes, we will use GLM to determine statistical differences in the primary outcome measures, while controlling for potential confounders and covariates associated with the selected outcomes. It should also be noted that missing results over time will be accounted for in the analysis using an inverse probability weighting scheme based on a logistic regression model.

References:

4. Barrett RK. Dialogues in diversity: An invited series of papers, advance directives, DNRs, and end-of-life care for African Americans. *OMEGA-Journal of Death and Dying*. 2006;52(3):249-261.
6. Escher Jr AR. An Ounce of Prevention: Coronavirus (COVID-19) and Mass Gatherings. *Cureus*. 2020;12(3).

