3.1. The ongoing or potential future public health restrictions (e.g., closures, physical distancing) has no impact on the research approach.

3.2. Multidisciplinary Investigators: One unique feature of this application is that the intervention be will implemented by a multidisciplinary team of community-faculty, church leaders, academic scholars, and health care providers. Our research team includes: an experienced gerontologist; an **AA community faculty** (who also is a church leader); **six AA** health care practitioners and researchers (an infectious disease specialist, a family medicine physician, a nursing specialist, a pharmacist, a community health prevention specialist, and a public health specialist).

3.1. Part One: Specific Aim 1 - Community Strategizing: To collaborate with 10 AA church leaders on implementing Federal and State (California) public health guidelines for churches for reducing COVID-19 risk in predominantly AA churches in South Los Angeles.

Implementation of Aim 1: We will employ various strategies to assist predominately AA churches with implementing and adhering to federal and state public health guidelines, which include 1) create a multidisciplinary taskforce with clergy members and church leaders to develop a surveillance protocol focused on COVID-19 infection prevention and measure progress of COVID-19 prevention efforts, 2) conducting environmental assessments and scans of churches to identify high risk infection areas, 3) developing culturally sensitive communication media and messages with clergy members to deliver to church parishioners, 4)

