Evaluation: There are various strategies we will employ to conduct evaluation and quality improvement for implementation of guidelines. We will work with clergy members to conduct bi-monthly assessments of church services by scoring specific elements of recommended guidelines for churches by surveying church leaders and observational assessment of each church's environment. Based on the environmental scans and the multidisciplinary taskforce, we will develop a checklist that will include, but not limited to assessment and observation of: 1) social distancing during worship services (i.e. no hugging, close seating), 2) use of face coverings by everyone in the church, 3) disinfection of facilities, 4) personal use of worship hymnals, Bible, and other items, 4) church staff preparedness of staff to identify signs and symptoms of infected individuals, 5) messaging during service regarding COVID-19. The results of bi-weekly checklist and survey will be shared with church leaders for modification of operations and analyzed after 6 months to evaluate adherence of COVID-19 prevention practices. As a result of this intervention, it is expected that the participating churches will meet or exceed 80% of the checklist criteria for the 6-month duration. Additionally, all questions received during the monthly seminars and telephone hotline will be ranked based on the quality as a criterion for improvement of COVID-19 knowledge and practice.

3.2. Part Two: Specific Aims 2 & 3 - Community Building and Sustainability and Individualized

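### Aim 1 credits the programme with churches reaching 80% of a checklist, but plans no checklist score before the programme, so the target can show a level of adherence and not a change

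*Combined protocol and SAP*

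**What the plan says.** The Combined protocol and SAP, section 3.1 Part One (Specific Aim 1), covers 10 churches: "To collaborate with 10 AA church leaders on implementing Federal and State (California) public health guidelines for churches".

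The Evaluation paragraph of that section sets the only numerical target for the aim: "participating churches will meet or exceed 80% of the checklist criteria for the 6-month duration". The sentence opens by crediting the programme: "As a result of this intervention, it is expected that the participating churches will meet or exceed 80" per cent.

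The same paragraph gives the measurement:

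- **Who scores:** "We will work with clergy members to conduct bi-monthly assessments of church services by scoring specific elements of recommended guidelines".
- **How:** "by surveying church leaders and observational assessment of each church's environment".
- **Where the checklist comes from:** "Based on the environmental scans and the multidisciplinary taskforce, we will develop a checklist".
- **Use of results:** "The results of bi-weekly checklist and survey will be shared with church leaders", so that they can adjust operations. An analysis follows after six months.

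The Implementation of Aim 1 paragraph lists the scans among the programme's own strategies, with this purpose: "conducting environmental assessments and scans of churches to identify high risk infection areas". The taskforce, which includes clergy and church leaders, is another of those strategies.

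The timeline table starts guideline implementation in months 1-3. Its only baseline row is for the older African American participants.

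**The concern.** The target is worded as an effect of the intervention but measured as a level. To speak of a result, one needs at least a starting value on the same instrument, and Aim 1 has none. The plan measures before and after elsewhere: advisors are surveyed before and after training, and Phase 2 of Part Two has a pretest-posttest design.

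The starting level could well be high for some churches. The section on COVID-19 and African American churches says that CDC and State reopening guidance had already been released. A church that had adopted most of it beforehand would be reported as a success of the study.

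The score also depends partly on the people being rated. Church leaders answer the survey, clergy help conduct the assessments, and both sit on the taskforce behind the checklist. Observation is part of the score, but the plan does not say who observes or how observed and survey answers are combined.

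What is at stake is the claim that Aim 1 can support. The study's powered primary outcome (poor adherence among older adults, Phase 2) is not affected.

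**Working it through.** **1. Is there a baseline anywhere in the text?** Four places could hold one.

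- *Environmental scan.* It identifies risk areas and feeds the checklist. It comes before the checklist exists, so it cannot be a score on it.
- *Taskforce.* It is to measure progress of prevention efforts, but no starting measurement is named.
- *Timeline.* Baseline data collection is listed for older adults only.
- *Analysis section.* The pretest-posttest comparison, McNemar test and paired t-test are set out under Sample Size and Data Analysis (Phase 2), not for Aim 1.

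None supplies a checklist score before the intervention. No comparison churches are planned either.

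**2. What does an 80% end score mean?** Change = 80 - b, where b is the starting score (assumed, since none is given).

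| Assumed start b | Change at an end score of 80% |
|---|---|
| 40% | +40 points |
| 60% | +20 points |
| 80% | 0 |
| 85% | -5 points |

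The same end score fits a large gain, no change or a small loss.

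**3. How often would the target be met with no effect?** The 80% is a stated benchmark with no derivation, so there is no figure of the plan's to reproduce. Let p be the probability that a church already meets 80% and stays there. Take the 10 churches as independent; p and independence are both assumptions. The plan does not say how many churches must succeed, so two readings are shown.

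- All 10: p^10.
- At least 8: 45 p^8 (1-p)^2 + 10 p^9 (1-p) + p^10.

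| p | All 10 | At least 8 of 10 |
|---|---|---|
| 0.5 | 0.001 | 0.055 |
| 0.8 | 0.107 | 0.678 |
| 0.9 | 0.349 | 0.930 |
| 1.0 | 1.000 | 1.000 |

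For p = 0.8 the second column is 0.302 + 0.268 + 0.107 = 0.678 (from unrounded terms). Nothing in the documents narrows p, so the range runs from near 0 to 1.

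**4. How many assessments?** One sentence calls them bi-monthly and a later one bi-weekly. Over six months:

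- every two months: 6/2 = 3;
- twice a month: 6 x 2 = 12;
- every two weeks: 26/2 = 13.

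Elsewhere the document uses bi-weekly for six sessions in three months, that is, about every two weeks. The count is therefore 3, or 12 to 13, depending on how bi-monthly is read. The text also does not say whether 80% applies at each assessment or to a church's mean.

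**The case against.** The best defence is that this is an implementation benchmark. Aim 1 is about putting guidelines into practice, the paragraph is framed as evaluation and quality improvement, and the 80% is not among the numbered hypotheses and has no test attached. An absolute level is a fair answer to whether churches adhere. That stands: 80% remains usable as a statement of adherence. It does not rescue the causal phrase.

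Four stronger readings are tempting, and the documents do not support them.

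- *Clergy rate themselves.* The research team works with clergy, and observation is included. The gap is that the observer is unnamed and survey and observation are not separated.
- *All scoring starts after the programme begins.* The first scoring has no date. It must precede any checklist feedback, since results are shared afterwards. Whether it precedes the seminars is not stated.
- *The two frequencies contradict each other.* If bi-monthly means twice a month, 12 and 13 nearly agree. The wording is ambiguous and not necessarily in conflict.
- *A baseline would prove an effect.* It would not. There are no comparator churches, and the section itself expects continual updating as infection rates and guidance change. Before-after change could come from that alone.

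**Conclusion.** The concern holds in a limited form. As written, reaching 80% can show the adherence level the churches attained. It cannot show that they changed, and still less that the programme caused a change. The first half rests on reading the text and needs no assumption: no checklist score before the intervention is planned.

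The size of the problem is unknown, because the documents give no starting adherence. The probabilities above depend on the assumed p, on independence between churches and on the assumed number of churches that must succeed. They illustrate the range and do not estimate it.

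The leader survey and clergy involvement leave room for favourable scoring, but the documents do not allow that to be sized. The unclear frequency and the undefined 80% rule mean that two analysts could reach different conclusions from the same data.

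The change is worth making because it is cheap and a missed baseline cannot be recovered.

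**What to change.** 1. Once the checklist is finished, hold the first scheduled assessment at each church before any checklist feedback or seminar.
2. Have research team members score the observable items at that assessment and at every follow-up, in the same way, so that a change of rater is not mistaken for a change in practice.
3. Report each church's change from that first score beside the 80% level.
4. Report observed items separately from leader-survey items.
5. Replace the causal phrase with wording that claims adherence and before-after change only.
6. State one assessment frequency, and say whether 80% applies to each assessment or to the church's mean.

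**Cost.** Items 3 to 6 are wording and tabulation. Item 1 moves an assessment already planned, but the checklist must be ready before seminars start. Because the checklist is built from the scans, the first scoring cannot be part of the scan itself, so a separate visit to each of the 10 churches may be needed. Item 2 takes observer time: 10 churches at 3, 12 or 13 assessments is 30, 120 or 130 observations, though the team already plans to take part. Items tied to in-person services can be scored only where services are running, and the report should say where they were not.

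If seminars or feedback have already begun, the before-after comparison is lost. Items 4 to 6 can still be done, with the claim limited to the adherence level reached. Clergy can continue to receive results and adjust operations throughout.

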Strategies to Train AA Advisors: The workshop training will occur bi-weekly over a 3-month period to prepare them for delivering the intervention to AA older adults. Detailed information on the content areas are described in **Table 1**. The training curriculum will cover the following components: 1) minimize risk of COVID-19 infection and transmission; 2) utilizing remote learning platforms to train older adults on effective use of telehealth; 3) gain extensive knowledge regarding COVID-19 and its impact on individuals with underlying chronic conditions; 4) identify over-reacting (obsessive) and under-reacting behaviors to COVID-19, physical and social distancing, and other measures; 5) assessment of social needs and consequences of long-term social isolation; 6) delivery of extensive knowledge regarding the importance of adherence to medication refills and regimens, as well as adherence to lifestyle recommendations for older adults with chronic conditions; 7) providing functional support to older adults, particularly those who are socially isolated, to manage their activities of daily living; 8) assisting older adults in the use of online services for making medical appointments, obtaining medication refills, etc. and finally, 9) learn administering survey and collect data from older adults. In addition, we will discuss the functions and role expectations of health advisors, including care coordination, health coaching, education, and assessment, social support, and case management and resource linking.^{112,113}

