Evaluation of Training: Following each training session, health advisors will complete a standardized survey that assesses the knowledge, self-efficacy, and skills for every workshop. If there are areas that are concerning to the research team based on the answers from health advisors, the subject topic will be repeated further explanation to the group. Within the last session, health advisors will demonstrate their training through a role-playing exercise. In addition, a structured survey lasting about 30 minutes which will be conducted at two time points (pre- and post- trainings) to evaluate church-based advisors' knowledge, attitude, and skills gained from the bi-weekly workshops over the period of 3 months. We will arrange the bi-weekly workshop sessions at times that are convenient to the trainers and trainees. All health advisors will be provided a monetary incentive (a total of \$200 for attending six 2-3 hours workshops) for participating in the program and completing study responsibilities for both phase 1 and 2 (see below). In addition, they will receive a certificate of completion and community recognition as church-based young adult health advisors for minority faith-based institutions. During the program ceremony commencement, three church-based young adult health advisors with the highest satisfaction scores will receive a \$1,000, \$500, and \$300 credit card gifts, respectively. Remediation will be conducted for those advisors who need additional assistance. As a result of this training, it is expected that AA advisors will: 1) score 90-100% on tests that assesses COVID-19 disease, transmission, symptoms, treatment prevention, and its impact on older adults with co-morbidities; 2) understand the use and application of telehealth, apps, and computer-based software to help AA older adults use telehealth and on-line services; 3) gain additional knowledge regarding the importance of adherence to medication refills and regimens, as well as adherence to life-style recommendations for older adults with chronic conditions; 4) support older adults,

particularly those with comorbidities or socially isolated, to manage their activities of daily living and assist them in the use of online services for making medical appointments, obtaining medication refills, etc.; and 5) learn to conduct survey and collect health-related data from older adults as a young adult health educator.

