Research Strategies for Phase Two: Recruitment: Recruitment of participants will be from the 10 collaborating churches in South Los Angeles. Recruitment will be conducted by our research team and church-based health advisors trained in phase 1 of this study. We aim to recruit a total of 265 AA aged 65 years and older parishioners. In addition to digital announcements publicizing the proposed project at respective churches, our research team member who is church leader (Reverend [name]) will assist clergy member to convene pre- or post-Sunday sermon meetings to introduce the program to the parishioners. They will also offer the contact information or referral to the church-based health educator, which will allow potential

Table 1. Group Intervention (IMB Framework)

Information	

 Explain COVID-19 sign & symptoms & treatment. How to minimize risk of COVID-19 infection & infecting others. Skills for COVID-19 self-assessment. When to seek medical advise. Explain connection between age, chronic conditions & COVID-19 risks. Discuss OTC, COM, & Alternative medicine. Timely screening for COVID-19 	
 Explain risks of non-adherence to disease surveillance & monitoring (i.e., lab tests, routine & required screening procedures, etc. Discuss high risk of non-adherence to medications Discuss new initiatives for home-based health care delivery Discuss Telehealth and its importance Discuss internet-based & mail order services (medication etc.)
Attitudes	

 Reduce anxiety & fear about COVID-19 Recognize & modify over-reacting (obsessive) & under-reacting behaviors to COVID physical & social distancing & other requirements. Discuss health status with nonadherence to medications (stroke, amputation, etc.). Appreciate social needs & consequences of long-term social isolation among older adults 	
 Modify cultural beliefs about testing, vaccination, & adherence to drug regimens & focus on culturally acceptable points that promote adherence. Enhance communication with providers in order to understand relevant information. Encourage the involvement of companions & family in illness management.
Motivations	

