criteria: A resident in a care facility and those with cognitive deficits (identified by short version of mini-mental state examination instrument). In addition, we will assess the participants' physical ability in terms of sight, hearing, and literacy (good, fair understanding, illiterate), which is necessary since this intervention will be conducted online and we will need to assess which participants may need additional support. Participants will be informed that this intervention will be conducted over three months and will involve three broad activities: 1) participation in pre-intervention (made up of Parts A and B) and post-intervention (made up of Part A only) surveys lasting about 100 and 50 minutes respectively. Part A will include validated measures of health, health

behaviors, healthcare utilization and other COVID-19 related variables. Part B will solely focus on dietary intake, access and physical activity utilizing validated instruments from DHQ-III, Food Insecurity (FI) and Yale Physical Activity (PA) surveys, respectively. (copies of the three additional questionnaires to be used in Part B of the pre-intervention survey are provided in **Appendices 1, 2 and 3**). Participants will be paid \$25 for each of the 2-part pre intervention survey and \$ 25 for the post-intervention survey; totaling a possible \$75 payment for completion of all three parts. Research staff will be trained and properly instructed to administer both parts of the survey.; 2) attendance at six bi-weekly online workshops that will provide targeted information on reducing risk for COVID-19; and 3) participation in individualized online visits with AA health advisors to discuss management of chronic conditions, in addition to receiving timely health assessment, coaching, and education.

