Intervention Strategies: We collaborate with AA church-based advisors trained in Phase 1 to deliver three-month longitudinal intervention to 265 older AA Parishioners. This intervention is composed of six 2-hour bi-weekly sessions that include lectures, discussions, followed by one-on-one “problem solving” consultations. Instead of an in-person approach, this intervention will be provided via telehealth. **Table 1** shows the curriculum of the proposed bi-weekly seminars/ intervention. This intervention uses a participatory, culturally sensitive, theoretical based (IMB), and multidisciplinary approach to reduce risk and enhance health for AA older adults. The longitudinal intervention includes: 1) Telehealth training; 2) COVID-19 risk reduction and testing; 3) health screening; 4) adherence to disease surveillance and monitoring (i.e., lab tests, routine and required screening procedures, etc.); 5) promoting adherence to medication refill and regimens; 6) promoting adherence to recommended life style behaviors; and 7) flu, pneumonia, & COVID (once available) vaccination.

Individualized Meeting: Trained health advisors will offer individualized monthly meetings to an assigned caseload of AA older participants, in addition to bi-weekly seminars, for individualized health assessments, coaching, and support meetings with the participants. The health advisors will assess the older participant's management of their chronic conditions by utilizing a standardized visit form during these meetings (for example, a diabetic patient must see and ere specialist every year – depending on type of chronic conditions, there is a standard recommendation for physician visits. They will also encourage and assist the participants in making appointments and/or facilitating communication with their primary care provider, getting their medication refilled, and getting tested for COVID-19. If the participant does not have a physician, we will provide a referral located in close proximity to the participant.

Informing Primary Care Providers: The primary care provider of participants will be notified in case of positive depression or high anxiety severity following screening; non-adherence to treatment or inability to access their treatment; and clinical presentation warranting emergent care. If the participant does not have a primary care provider, they will be referred to a one that is located in proximity of their location.

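### Could a participant's own coach end up administering the post-intervention survey?

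*Combined protocol and SAP*

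**What the plan says.** Under *Strategies to Train AA Advisors*, the ninth component of the curriculum is that advisors "learn administering survey and collect data from older adults". *Evaluation of Training* repeats this as an expected result: advisors will "learn to conduct survey and collect health-related data from older adults as a young adult health educator".

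In Phase 2 the advisors have several roles. They help to recruit: "Recruitment will be conducted by our research team and church-based health advisors trained in phase 1 of this study". They lead the bi-weekly seminars. Under *Individualized Meeting*, "Trained health advisors will offer individualized monthly meetings to an assigned caseload of AA older participants", and they assess chronic-disease management "by utilizing a standardized visit form during these meetings".

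The outcome surveys are described in *Research Strategies for Phase Two: Recruitment*. The pre-test consists of Parts A and B, and the plan describes the "post-intervention (made up of Part A only) surveys lasting about 100 and 50 minutes respectively". On who administers them it says: "Research staff will be trained and properly instructed to administer both parts of the survey".

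The analysis is a single-group pretest–posttest, "comparing our outcomes before and after the intervention, with a three-month interval", with McNemar's test for binary outcomes. The primary outcome is poor adherence, with an assumed 36% relative change from a 22% baseline and 240 analysable participants.

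**The concern.** Read quickly, two parts of the plan seem to pull apart. One trains the advisors to survey older adults; the other gives the surveys to research staff, a term used once and not defined. The plan does not state whether advisors count as research staff, and it does not forbid an advisor to interview someone they coach.

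The design makes this worth checking. There is no control group. Adherence is one of the behaviours the advisors are there to promote. The plan names no objective source for it, so it is presumably self-reported in Part A, which covers health behaviours. A participant who has had three months of coaching may be reluctant to tell the coach that doses or refills were missed. Because advisors also recruit, some of this could occur at the pre-test too, but the part created by coaching would fall only on the post-test. McNemar's test and the planned regressions could not separate it from a real effect, and it could not be repaired after data collection.

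**Working it through.** **Step 1. Who is assigned what.**

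| Task | Assigned to | Section |
|---|---|---|
| Recruitment | Research team and advisors, named as two groups | Research Strategies for Phase Two: Recruitment |
| Pre-test (Parts A and B) and post-test (Part A) | Research staff | Same section, first of three participant activities |
| Individualized visits | Health advisors | Same section, third of three activities |
| Standardized visit form | Health advisors | Individualized Meeting |
| Seminars | Advisors, with a specialist | Church-based Health Advisors and our Health Practitioner to Deliver Seminar and Workshop (Phase 2) |

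The post-test is Part A only, so an assignment that covers both parts covers the post-test. The list that assigns the surveys uses one label for those who administer them and another for those who hold the visits.

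**Step 2. Are advisors staff anywhere else?** Under *Design for Phase One of Part Two* they are enrolled by the study. Under *Evaluation of Training* they are trainees whose answers the research team reviews, who are themselves surveyed before and after training, and who receive an incentive and a certificate. The plan calls them advisors or educators and never staff.

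**Step 3. Does the survey training imply another assignment?** It has other uses in the plan: the individualized health assessments, the standardized visit form, and the stated aim of leaving trained advisors in the churches afterwards. No section assigns the pre- or post-survey to an advisor.

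**Step 4. How much would depend on it?** This is an illustration on assumed shifts.

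Inputs from *Sample Size and Data Analysis (Phase 2)*: n = 240, alpha 0.05 (taken as two-sided), baseline 22%, planned change 0.36 × 0.22 = 0.0792, or 7.9 points.

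Let D be the proportion of discordant pairs and δ the net shift. The rejection probability is approximately

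Φ[(δ√n − 1.96√D) / √(D − δ²)] + Φ[(−δ√n − 1.96√D) / √(D − δ²)].

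*The plan's own figure first.* The plan gives no D. With δ = 0.0792 and n = 240, this formula returns 80% power at D = 0.194. The textbook (Rosner) form gives a similar D of 0.201. So D = 0.194 is close to what the stated sample size implies.

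*A worked case.* No true change, a 3-point reporting shift, D = 0.194:
- δ√n = 0.03 × 15.49 = 0.465
- 1.96√D = 1.96 × 0.4405 = 0.863
- √(D − δ²) = √0.1931 = 0.439
- First term: Φ(−0.907) = 0.182. Second term: about 0.001. Total 0.183.

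Rejection probability with no true change:

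| Net shift | D = 0.10 | D = 0.194 | D = 0.343 |
|---|---|---|---|
| 1 point | 0.078 | 0.064 | 0.058 |
| 3 points | 0.311 | 0.183 | 0.124 |
| 5 points | 0.690 | 0.420 | 0.262 |

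D = 0.343 is independence at 22% (2 × 0.22 × 0.78). D = 0.10 corresponds to a pre/post correlation of 1 − 0.10/0.343 = 0.71, at the high end. If coaches did only half the post-tests, the average shift halves: at D = 0.194, 1.5 points gives 0.082 and 2.5 points gives 0.142.

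**Step 5. What the table assumes.** Advisors interview despite the assignment in Step 1; each interviews their own caseload; this happens for all 240 post-tests; and who asks moves answers by 3 to 5 points over and above any desirable answering to staff. No document supports the first three, and none gives a value for the fourth.

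**The case for a change.** The best case for a change is that the silence is real and closing it costs almost nothing. Advisors are paid for unspecified duties in both phases. The training sections speak of surveys, not only of forms, and the pre- and post-intervention surveys are the main older-adult surveys the plan describes. The sentence that names the research team and the advisors separately is about recruitment. A fieldwork manager short of interviewers could use the advisors without breaking any explicit rule, and in an uncontrolled design the harm would be permanent. If staff already do every interview, one sentence settles it. If not, the extra staff time is at most 265 × 50/60 = 221 hours for the post-test, or 265 × 150/60 = 663 hours for both surveys.

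Part of this stands: the term is undefined and there is no express prohibition. The rest does not carry it to a needed change. The separation of roles does not hang on the recruitment sentence; the survey section itself draws it, and the training sections treat advisors as people the study enrols and assesses. The hours arise only if the plan's own assignment is set aside. Excluding coaches would also leave untouched whatever desirable answering coached participants give to staff, which is a limitation of an uncontrolled comparison that relies on self-report.

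**Conclusion.** No change to the plan is needed. Where one section trains people in a skill and another assigns the task to a different group, the assignment governs. On the plan as written, research staff administer both the pre-test and the post-test, and the route to bias by coach-interviewers does not open. What is left is a missing definition that those running the study would fill sensibly by reading the survey section as it stands. A clarifying sentence would be tidy, but it would only restate an assignment already made and would alter no estimate, test or sample size.

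The conclusion rests on reading research staff as excluding the advisors, which the surrounding text supports but does not spell out. If advisors did in practice survey their own caseloads, the concern would be serious: at the discordance implied by the plan's sample size, false rejection would be about 18% for an assumed 3-point shift and 42% for 5 points, against about 6% for 1 point and a nominal 5%. Those figures describe a departure from the plan and are not a defect in it.
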